Aim 1: Analyses 1a-1c identify brain and psychological predictors of placebo analgesia, respectively. Placebo effects will be defined as Control vs. Placebo ([C – P]) differences in pain report (“placebo analgesia”) and two validated, pain-related brain measures: the NPS and SIIPS. These analyses will allow us to identify common and differential brain predictors of placebo effects on behavioral (pain report)

and neurobiological outcomes. They will permit three other novel tests: (1) Whether predictive patterns generalize across thermal and mechanical pain; (2) Whether they generalize across placebo effects in suggestion alone or post-conditioning; and (3) Whether we can identify latent factors across outcomes (thermal/mechanical, suggestion/conditioning), and develop predictors of those domain-general outcomes. Such factors are more likely to be genetically determined and useful in broader clinical contexts.

Multiple comparisons and power:

This study is the first large-scale study powered for *whole-brain analyses* of structural and functional correlates of placebo analgesia with Family-Wise Error Rate (FWER) map-wise correction. We will use FWER correction as implemented in Statistical Nonparametric Mapping (SnPM)⁴²³. This correction is valid, makes minimal assumptions, and is not affected by recent findings of inflated false positive rates with some correction methods⁴²⁴. With our sample size ($N = 600$), we have 80% power with whole-brain FWER correction to detect correlations with placebo analgesia of $r \geq 0.22$, which is within the range of our previous cross-validated estimates^{37, 268, 269, 353, 354, 369}.

Previous studies have been substantially underpowered; with $N = 50$, which is larger than most placebo studies, correlations must be $r = 0.65$ or larger to be detectable with 80% power. Though this is the first study adequately powered for whole-brain correction, we will also focus on testing hypotheses derived from the previous literature, as described below.

Analysis 1a identifies functional brain predictors of placebo analgesia. We focus on two systems related to placebo analgesia^{35, 409} (**Fig. 1a**): A **fronto-parietal system** involved in executive control and cognitive appraisal of emotion⁴²⁵⁻⁴³¹, and a **medial cortical-striatal-brainstem system**—including mid-lateral OFC, vmPFC, VS/nAC, and PAG. We hypothesize that behavioral analgesia will be related to anticipatory fronto-parietal activity and down-regulation of SIIPS responses (related to endogenous brain contributors to pain), but not modulation of the NPS (related to nociceptive pain), indicating that reported analgesia is influenced by decision bias and providing brain correlates of this bias.

Alternatively, analgesia may be correlated with NPS modulation and reductions in local targets of nociceptive afferents (S2, dpINS, mid-INS, aMCC), validating pain report as a predictor of neurobiological placebo effects. Increases in the medial system may also predict larger placebo effects on the NPS, linking this system to strong control of pain in placebo-responsive individuals.

Analysis 1b identifies structural brain predictors of placebo analgesia. We hypothesize that gray-matter density in the **medial cortical-striatal-brainstem system**, particularly nAC and vmPFC, will predict larger placebo responses in pain report, NPS, and SIIPS responses. Prior work suggests that gray-matter

| | Predictors | Outcomes: Placebo vs. control in |
|----|---|--|
| 1a | fMRI before, during pain, placebo vs. control | Placebo analgesia outcomes: 
 Pain report Pain-related fMRI 'signatures' (NPS, SIIPS) Separately for thermal, mechanical pain Separately for suggestion vs. conditioning Factor scores across these outcomes |
| 1b | Structural MRI | |
| 1c | Personality and behavior | |
| 2a | Twin status: Monozygotic vs. Dizygotic vs. unrelated Structural model | 
 Heritability of pain report, NPS, SIIPS Frontoparietal, Medial frontal-brainstem network increases |
| 2b | Twin status (mono/dizygotic) Genetic correlations | Heritability of correlations between placebo outcomes and predictors from Aim 1 |
| 2c | SNPs from candidate gene families | 
 Placebo outcomes Predictors from Aim 1 |
| 3a | Polygenic risk scores (PRS) in ENIGMA consortium | Regress placebo-linked structural features on SNPs in ENIGMA, yielding PRS. Test in Women's Health Initiative study. |

Table 1. Overview of analyses

density in the hippocampus^{432, 433} and fronto-parietal system²⁷³ may also be related to placebo effects. Diffusion-weighted imaging (DWI) will be used to assess the size/integrity of fiber tracts. We expect placebo effects to be associated with tracts connecting the vmPFC and OFC with the PAG²⁶¹; but **alternatively**, connectivity in the fronto-parietal system (esp. dlPFC) and lateral frontal-brainstem connectivity may be more predictive. Such findings would connect placebo effects to systems involved in value and motivation, on one hand, or cognitive control on the other. This would permit evaluation of the parallel between pain regulation and other forms of cognitive regulation, and connect placebo effects with systems that degrade with age and dementia.

Analysis 1c will test whether placebo effects on behavioral and brain measures of analgesia are related to personality and behavioral measures that can be easily assessed clinically. We will apply confirmatory factor analysis to web-based assessments to identify latent factors⁴³⁴ related to (a) susceptibility to perceptual/decision bias (i.e., influences of instructions on judgments of shape, color, etc.); (b) positive vs. negative interpretations of ambiguous events; (c) latent variables related to task switching, inhibition, and working memory identified in our previous work³³¹⁻³³⁶; and (d) personality measures, focusing on an “optimistic/pro-engagement” style and an “anxious” style. We will conduct five-fold cross-validated analyses⁴³⁵⁻⁴³⁷ developing an optimal combination of behavioral variables for predicting placebo analgesia. We expect that placebo analgesia will be related to **(a)** larger perceptual/decision biases²⁸², **(b)** high optimism⁴³⁸, and **(c)** low anxiety and fear of pain²⁹¹⁻²⁹³. We are agnostic about whether cognitive control measures will predict placebo analgesia, but it is important to know either way; some studies suggest placebo effects are related to cognitive control^{438, 439}, whereas others suggest they are distinct forms of motivation-based regulation^{257, 440}. Positive results from Analysis 1c will provide a behavioral phenotype that can be readily assessed in clinical settings. We can then relate these behavioral measures to brain measures, as in Analysis 1a, to link them to neurobiology. Negative results will also be very important, as several companies are currently investing in personality-based predictors for clinical settings. The field needs to know whether or not such measures are viable predictors of placebo response magnitude.

Extensions and alternative plans. (1) We are developing new large-sample predictors of pain, and will test those as they become available. (2) Another important extension relates to individual differences in pain sensitivity. While not the main focus here, this dataset and our approaches are well-suited to predicting individual differences in pain sensitivity—a core feature of many pain conditions⁴⁴¹⁻⁴⁴³ and a risk factor for later chronic pain⁴⁴⁴⁻⁴⁴⁶. Models of risk for chronic pain following surgery (unfortunately common) and other procedures would be a crucial advance in precision medicine⁴⁴⁷⁻⁴⁵². Risks can be assessed at both phenotypic (predicted by evoked pain sensitivity) and genetic⁴⁵³ levels. Exploratory analysis will allow us to develop a foundation for understanding the neurobiology of individual differences in pain sensitivity.

Aim 2: Analyses 2a-2c will assess the heritability of placebo effects and placebo-predictive brain features, and relate these features to candidate gene families. **Analysis 2a (Aim 2.1)** identifies the heritability of placebo effects in pain report and brain responses for the first time. We hypothesize that heritability of pain reports will be modest, but heritability of placebo modulation of specific pain-related brain measures (the NPS and SIIPS) will be stronger, as these reflect component systems that are less etiologically complex and less context-sensitive than overall pain report. We also expect heritability to be high for gray-matter density in nAC and hippocampus⁴⁵⁴, and mPFC-brainstem pathways. The **model** for analysis 2a is a standard univariate ACE model^{455, 456}, which decomposes twin covariances for a trait of interest into additive genetic (A), shared environmental (C), and non-shared environmental (E) variance

components (Fig. 5). This model will be applied to individual placebo measures (e.g., thermal and mechanical pain), and also to latent variables (i.e., using a common factor model with thermal and mechanical pain loadings constrained to equality to identify the factor).

Analysis 2b (Aim 2.2) identifies genetic correlations between placebo effects and brain features that predict them. It tests whether individuals who are more genetically related show higher cross-twin, cross-trait correlations. The model for this analysis is a bivariate extension of the ACE model^{455, 456} (Fig. 5b). The covariance between two measures is decomposed into genetic and environmental components with a Cholesky decomposition. The ACE variables for the first measure (e.g., placebo analgesia) are allowed to predict the second trait, and the second trait is allowed to have unique ACE influences. Of primary interest for **Aim 2.2** is the genetic correlation (rA) of the two phenotypes, which indicates the extent to which the genetic influences overlap across the two traits: $rA = a_{12}/\sqrt{a_{12}^2 + a_{22}}$; rC and rE can also be computed analogously. We will apply this model to relationships between analgesia and pain neurophysiology (i.e., NPS and SIIPS), and functional and structural features that predict placebo effects (e.g., nAC density, fronto-striatal activity). We expect the strongest genetic correlations in structural MRI measures that are likely highly genetically determined⁴⁵⁷. Structural features that are both placebo-linked and genetically associated with placebo (e.g., nAC gray-matter density) are good candidates for polygenic risk scores in Aim 3. **Power:** Assuming a moderate E variance of 30%, we will be able to detect genetic variance as low as 34% and shared environmental variance as low as 36% with >80% power. With an E variance of 40%, we can detect an A of 45% and C of 40% with >80% power. **Genetic correlations:** We will have power to detect either an rA or rC in the presence of an rE : Assuming 40% A and 30% C and E variances for both variables, we will be able to detect rAs of at least .36 and rEs as low as .22 with >80% power. Assuming 40% C and 30% A and E variances for both variables and correlations between both Cs and Es, we will be able to detect an rC of .34 and rE of .19 with >80% power.

In **Analysis 2c**, we will attempt to replicate previously identified associations between candidate genes and placebo effects (reviewed in ³⁷⁶). We expect the most meaningful results to come from polygenic risk scores (see below), but it is important for the field to know whether the candidate genes already identified predict placebo responses or not. Based on previously reported associations, our study is well powered to determine this. We focus on SNPs within (+/- 10 kb of gene boundaries) several neurotransmitter/ neuropeptide gene families previously linked with placebo analgesia in pharmacological and molecular imaging studies, including **catecholamine and monoamine clearance** (COMT, MAO-A), **opioids** (OPRD1, OPRM1, OPCML, SIGMAR1, OPRK1, PDYN, OGFR), **dopamine** (DBH, DRD5, PPP1R1B, DRD1, SLC6A3, DRD4, DRD2, DRD3, CALY), **serotonin** (5-HT; HTR[1-3]A/B, HTR[1-3]B, HTR1[D-F], HTR2C, HTR3C/D/E, HTR5A/B, HTR[4, 6, 7], MAOA, SLC6A4), **cannabinoids** (CNR1, CNR2, CNRIP1), and **cholecystokinin** (CCK; CCKAR, CCKBR, CCK, DBI), and BDNF. We will test for statistical enrichment in SNP associations within these gene families using the MAGMA

[figure not shown]
[figure not shown]

Figure 5. Structural ACE model for heritability. Circles: latent variables for the genetic (A), shared environmental (C), and unique environmental (E) influences for each twin in a pair. MZ: monozygotic; DZ, dizygotic. The correlation between the genetic effects (A) is set to 1.0 in MZ twins and 0.5 for DZ twins (who share on average half their segregating genes). All twins are reared together in our sample, so C is set to 1.0 in both groups, and E is set to zero because unique influences are unshared, by definition. Right: Bivariate extension for estimating genetic correlations. nAC: nucleus accumbens, an example candidate region.

[doi:10.1371/journal.pcbi.1004219] and VEGAS [http://dx.doi.org/10.1016/j.ajhg.2010.06.009] software tools. This set comprises 48 genes with an estimated 320 genotyped SNPs and 4800 imputed SNPs with MAF > .005. Most of these SNPs do not exist on the Affymetrix Axiom Precision Medicine chip, but they can be imputed with excellent fidelity from genotyped SNPs using the Haplotype Reference Consortium reference sequence database [doi:10.1038/ng.3643], which has replaced the 1kG reference database as the gold standard. This approach is now standard for GWAS. We estimate imputation of ~97% of candidate SNPs with ~99% accuracy using the *MACH* program⁴⁵⁸. **Power:** Assuming correction across ~50 candidate genes, we will have 80% power to detect effects of $d = 0.24$ ("small") or greater, substantially smaller than most previously reported associations. **Hypotheses:** Previous studies reported that opioid genes were related to fMRI signal in PAG and vmPFC⁴⁵⁹⁻⁴⁶¹; dopamine genes to enhanced placebo after conditioning, compared to suggestion alone^{462, 463}; and serotonin and CCK genes to (a) anticipatory activity in vmPFC, which correlates negatively with placebo analgesia^{63, 70, 464} and positively with anxiety⁴⁰⁸, and (b) activity in the serotonergic dorsal raphe nucleus (adjacent to the PAG), which is activated in placebo studies^{162, 403, 465, 466} and is linked to threat and analgesia in animal models⁴⁶⁷⁻⁴⁶⁹.

Aim 3: Analysis 3. These analyses will develop Polygenic Risk Scores (PRSs) for placebo-linked brain structural features in the ENIGMA consortium dataset (**Fig 6**). The ENIGMA consortium is the world's largest study of relationships between brain structure and GWAS⁴⁷⁰. ENIGMA contains no personally identifiable information; investigators share summary statistics from analyses back to the requestor, in this case the [name] Lab. As such, it is a meta-analysis and does not involve sharing of identifiable data which could be linked to participants. In **Aim 3**, we leverage the information provided by the smaller, pain- and placebo-phenotyped twin sample to take advantage of the information in the larger, but less extensively phenotyped, consortium sample. Structural brain features with the highest genetic correlations with placebo response in our study—e.g., gray-matter density in nAC, vmPFC, and hippocampus—will be extracted from T1 data and regressed on GWAS SNP data in the ENIGMA sample. We estimate including at least $N = 10,000$ individuals, with a target of $N = 30,000$. PRSs will be developed by regressing individual SNPs on structural features using linkage disequilibrium (LD) regression^{471, 472} as implemented in the PLINK package⁴⁷². Regression weights on SNPs comprise a model that can be applied to new GWAS data to calculate an individual's aggregate genetic risk¹³⁰. We employ several choices shown to be advantageous, including using a wider set of SNPs in the model^{472, 473} and pruning SNPs in linkage with the strongest signals (e.g., $r^2 > 0.05$)^{130, 474}. Finally, to estimate the effects of this PRS on placebo responses, we will correlate PRSs with clinical placebo responses in the Women's Health Study ($N = 5,800$

with GWAS data) in collaboration with Consultant [name]. Testing aggregate risk involves only a single test, with >80% power to detect even extremely small relationships (e.g., $r^2 = 0.002$) between PRS scores and placebo responses.

Extensions and alternative plans. (1) While we expect ENIGMA to be an outstanding resource for these analyses, other options exist. The UK Biobank recently released its first 10,000 participants⁴⁷⁵, and

it includes structural and diffusion imaging and GWAS; similar to the ENIGMA consortium, UK Biobank data is de-identified and cannot be linked to individual participants. The ENIGMA consortium have access to this data. **(2)** In addition to LD models for PRS development, we will explore using the machine learning models used for the main fMRI analysis, adapted for binomial allelic outcomes (5-fold cross-validation stratified by data-collection site, modeling covariance across twins). This will allow us to train models on a subset (4/5) of the twin sample, train PRSs on the ENIGMA sample, and then “back-validate” the relationships with placebo effects on an independent (1/5) of the twin sample. This will also let us identify psychological/behavioral correlates the PRSs in the twin sample. **(3)** Finally, new informatics methods are actively being developed to conduct more elaborate analyses on the ENIGMA data. As these methods become available, another extension is to run cross-validated analyses identifying more complex patterns of structural changes in the twins, identifying PRSs in ENIGMA, and back-validating in independent subsets of the twin data. **(4)** We will conduct standard GWAS with whole-genome correction ($p < 5e-8$) further corrected for number of brain variables, with 80% power to detect SNPs correlated at $r^2 > .006$, as well as the 6 gene families discussed above, with virtually perfect power to detect SNPs with even extremely small effects ($r^2 > .006$).

A.4 Data acquisition and model specifics

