
pain^{406, 495-498}. Event timing optimized using a genetic algorithm (GA)⁴⁹⁹, design efficiency evaluated for each individual. *Second level:* (1) Voxelwise hierarchical mixed-effects modeling with restricted iterative generalized least squares (rIGLS)⁵⁰⁰ accounting for correlated errors across DZ/MZ twins; or (2) multivariate machine learning models.

The scanning portion of the study will take place at the Intermountain Neuroimaging Consortium at the Center for Innovation and Creativity at [name]. The MRI device for these scans is FDA approved for research with human subjects and has all the safety inherent in a clinical MRI scanner. The radio frequency fields conform to guidelines determined by the FDA and the FDA has designated MRI scanners to be a non-significant risk device. MR techniques non-invasively produce images and measurements from tissues in the intact, living human.

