Statistical learning framework for fMRI and molecular genetic analyses. In contrast to typical voxel-wise mapping fMRI analyses and SNP-by-SNP GWA analyses, multivariate predictive models predict outcomes as a combination of (pattern across) multiple voxels/SNPs. This model yields an aggregate predictive score based on all available brain/SNP information, which is validated by applying it to new individual test subjects. Placebo analgesia ($[C - P]$ in pain report) and changes in pain-related NPS and SIIPS responses ($[C - P]$) are the outcomes to be explained. We use LASSO-PCR⁴⁰⁸ or Least Absolute Shrinkage and Selection Operator⁵⁰¹ Principal Components Regression (Fig. 2; this compares favorably with popular support vector regression). *Data reduction:* principal components analysis retaining $N-2$ orthogonal predictors; *Penalized regression* of component scores onto the outcome uses LASSO shrinkage, simplifying the model. *Cross-validation* is five-fold, balanced cross-validation⁵⁰² in discovery sample ($N = 500$), with $N = 100$ reserved as a final test set⁴³⁵. These methods provide stable, robust estimates when there are more predictor variables (voxels or SNPs) than observations, and account for covariance among predictors (i.e., linkage disequilibrium in SNPs⁵⁰³). In addition, feature (variable) selection using our prior work on placebo analgesia⁴⁰⁸ will simplify the models and increase interpretability. *Tests of voxel and SNP importance* will be accomplished using a null-hypothesis permutation test^{408, 423, 504} ($p < 0.05$ FWER). In *molecular genetic* analyses, feature selection will be accomplished by (a) focusing on polymorphisms related to six key placebo-linked gene families, or (b) optimizing the inclusion threshold and sparsity⁵⁰³ via nested cross-validation.

Study timeline

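### The permutation tests behind the whole-brain and importance FWER claims specify no scheme that respects the 300 twin pairs, and the 80% power figure makes no allowance for pairing.

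*Protocol*

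**What the plan says.** Section IV of the protocol recruits 600 twins as 300 same-sex pairs, 150 monozygotic (MZ) and 150 dizygotic (DZ). Sections V and VII give about 700 (350 pairs).

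Under A.3, Multiple comparisons and power, the whole-brain method is: "We will use FWER correction as implemented in Statistical Nonparametric Mapping (SnPM". The same paragraph says: "This correction is valid, makes minimal assumptions, and is not affected by recent findings of inflated false positive rates" seen with some other methods. With N = 600 it then claims that "we have 80% power with whole-brain FWER correction" for correlations of 0.22 or more, and adds that with N = 50 "correlations must be $r = 0.65$ or larger to be detectable with 80% power".

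Under A.4, Statistical learning framework, testing of voxel and SNP importance "will be accomplished using a null-hypothesis permutation test" at FWER 0.05.

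Twin structure is addressed in three other places:
- The A.4 second-level fMRI model offers a voxelwise mixed model (rIGLS) "accounting for correlated errors across DZ/MZ twins", with multivariate machine learning as the alternative.
- An extension under Aim 3 models twin covariance when building polygenic scores.
- The SAP puts familial random effects, by zygosity, in the thermal pain rating model.

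None of these says how permutations are restricted, or how the rIGLS model and SnPM are combined.

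**The concern.** A permutation test is valid when the shuffled units are exchangeable under the null. Members of a twin pair are not exchangeable with members of other pairs. Shuffling individuals freely breaks the pairing, so the permuted statistics vary less than the real null statistic does whenever predictor and outcome are both correlated within pairs. The threshold is then too low.

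The protocol itself expects that condition. Analysis 2a anticipates high heritability for some gray-matter measures, modest heritability for pain report, and stronger heritability for placebo modulation of the NPS and SIIPS, which are also Aim 1 outcomes. For SNPs the predictor is familial by construction: the Figure 5 caption gives genetic sharing of 1.0 in MZ and 0.5 in DZ pairs.

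At stake is the claim that these are the first adequately powered, family-wise-corrected maps of placebo analgesia, and the credibility of the importance tests on the predictive models.

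**Working it through.** **1. Reproduce the stated power.** The protocol gives no voxel threshold, so it has to be back-solved. With power = Φ(atanh(r)·√(N−3) − z_crit), r = 0.22 and N = 600:
- atanh(0.22)·√597 = 5.465, so 80% power implies z_crit = 5.465 − 0.842 = 4.62 (two-sided p = 3.8 × 10⁻⁶).
- At that threshold N = 50 needs r = tanh(5.465/√47) = 0.66, against 0.65 stated.

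The two stated points roughly agree, and both count people as independent.

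**2. Effect of pairing on an unweighted correlation.** For equal numbers of MZ and DZ pairs, the null variance of r is multiplied by

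VIF = 1 + ½(ρx,MZ·ρy,MZ + ρx,DZ·ρy,DZ),

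where x is the brain measure and y the placebo response. Only one set of twin correlations comes from the protocol: the 40% A, 30% C, 30% E example in the Analysis 2b power statement gives 0.40 + 0.30 = 0.70 (MZ) and 0.20 + 0.30 = 0.50 (DZ). The others are assumptions.

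**3. FWER under free shuffling.** A 5% FWER at p = 3.8 × 10⁻⁶ corresponds to M = ln(0.95)/ln(1 − p) ≈ 13,568 effective tests. Then FWER = 1 − (1 − p′)^M, with p′ the two-sided tail at 4.62/√VIF. For VIF 1.37, 4.62/1.17 = 3.95, p′ = 7.8 × 10⁻⁵ and FWER = 65%.

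**4. Power at r = 0.22 with a valid null.** Unweighted: Φ(5.465/√VIF − 4.62). Twin-weighted (GLS): Φ(5.465·√g − 4.62), where g is the MZ/DZ average of (1 − ρxρy)/(1 − ρy²).

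| Twin r, brain (MZ/DZ) | Twin r, placebo | VIF | Free-shuffle FWER, analytic | Free-shuffle FWER, simulated | Power, unweighted | Power, GLS | Power, unweighted, N = 700 |
|---|---|---|---|---|---|---|---|
| .80/.40 | 0/0 | 1.00 | 5% | 4% | 80% | 80% | 90% |
| .20/.10 | .20/.10 | 1.025 | 6.5% | 9% | 78% | 80% | 89% |
| .30/.15 | .30/.15 | 1.056 | 9% | 9% | 76% | 80% | 87% |
| .70/.35 | .30/.15 | 1.131 | 17% | 10-14% | 70% | 73% | 82% |
| .80/.40 | .34/.17 | 1.170 | 23% | 20% | 67% | 70% | 80% |
| .70/.50 | .70/.50 | 1.370 | 65% | 33-45% | 52% | 80% | 66% |

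The simulations used 150 MZ and 150 DZ pairs and 600 to 2,000 independent null voxels, with a maximum-statistic test of an unweighted correlation. The inflation grows with the number of voxels: in the last row it is 33% with 600 voxels, 45% with 2,000, and 65% at the analytic 13,568.

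**5. SNPs.** With 1,000 null SNPs, unweighted statistics and free shuffling, simulated FWER was 16% for placebo twin correlations of .30/.15 and 13% for .20/.10.

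**6. Two remedies.** Permuting whole pairs within zygosity, with within-pair swaps, gave 3-8% in the voxel scenarios (Monte Carlo SE about 1.1 points) and about 5% for SNPs. A twin-weighted GLS statistic refitted in each free permutation (1,000 voxels) gave 4.5-5.5% with .70/.50 on both traits, against 43% unweighted. With .70/.35 and .30/.15 it gave 5.0-6.1%, against 13% (SE of the GLS figures about 1.5 points).

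**7. Detectable r at 80% power, N = 600, valid null.** r = tanh(5.465·√(VIF/597)): 0.223 at VIF 1.025 and 0.256 at VIF 1.37. A GLS model with equal familial correlations (g = 1) stays at 0.22.

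**The case against.** The strongest reply is that the protocol already plans a voxelwise model for twin-correlated errors. Step 6 bears this out: if that model supplies the statistic and is refitted in each permutation, even free shuffling holds about 5%. A reader might infer that the twin-aware model corrects the voxel statistic and leaves the threshold wrong; the calculation does not support that. What remains is that no section connects the model to SnPM, and that it is only one of two second-level options.

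Three further stronger readings also fail:
- **That the plan shuffles twins freely.** No section says so. This would be an inference from silence, and the team models pairing elsewhere.
- **That the error rate is 45% or 65%.** Those figures need the 40/30/30 variances, which the protocol uses only to illustrate power for genetic correlations. It expects modest heritability for pain report.
- **That 80% power will not be delivered.** The 52-78% range belongs to an unweighted correlation with a corrected threshold. Under free shuffling power would barely move (76-80%), so inflated error and a large power loss cannot both be claimed for the same analysis. Enrolling about 700 would offset part or all of the loss.

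It is also fair that the SAP's main thermal pain analysis is untouched, and that features for Aim 3 are chosen by genetic correlations from models with explicit MZ/DZ structure. The LASSO-PCR weights were not simulated, so the evidence for the importance tests is the SNP simulation and the general argument.

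**Conclusion.** The point holds as a gap in specification with a measurable consequence. The claim of validity is unsupported for this sample until the permutation scheme is stated. The gap matters most for the LASSO-PCR and SNP importance tests, which the twin-aware voxelwise model does not reach.

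If shuffling is free and statistics unweighted, FWER runs from about 6.5% (weak familiality), through roughly 10-20% (heritable structural maps, or SNPs with a moderately familial placebo response), to 33-65% under the 40/30/30 example. It stays at 5% if the placebo response is not familial. Apart from that example and the genetic sharing of SNPs, the twin correlations are assumed, and the analytic values take every voxel to have the stated correlation.

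Separately, 80% power at r = 0.22 with N = 600 makes no allowance for pairing. With a valid null it is about 52-78% unweighted and 70-80% twin-weighted, at the implied threshold of z = 4.62.

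**What to change.** In A.3 (Multiple comparisons and power) and A.4 (Statistical learning framework), specify the permutation scheme: permute whole pairs within zygosity, swap members within pairs at random, and keep the same maximum statistic. Apply it to voxel maps, LASSO-PCR weights and SNP importance. For voxel maps an acceptable alternative is the A.4 twin-aware statistic refitted in every permutation; if that is intended, say so and state how rIGLS feeds SnPM.

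Restate the detectable correlation with the assumed twin correlations, the voxel threshold and its sidedness, the estimator, and one sample size (600 or 700). At N = 600 and the implied threshold it will be about 0.22 to 0.26.

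The cost is a few sentences, a different shuffling routine or more computing for refits, and a slightly less favourable stated figure. No additional data are required.

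### Analysis 1a would read a SIIPS-but-not-NPS result as a sign of decision bias, but names no test that the two relations differ and no threshold for them

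*Protocol*

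**What the plan says.** Protocol section IV, A.3, Analysis 1a, gives the leading hypothesis: "We hypothesize that behavioral analgesia will be related to anticipatory fronto-parietal activity and down-regulation of SIIPS responses", "but not modulation of the NPS (related to nociceptive pain), indicating that reported analgesia is influenced by decision bias". The next paragraph gives the rival: "Alternatively, analgesia may be correlated with NPS modulation and reductions in local targets of nociceptive afferents". That result would be taken as validating pain report as a predictor of neurobiological placebo effects. The NPS finding therefore helps decide which of two opposed mechanistic readings is reported, and one of them needs an absent relation.

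The nearest text to a comparison is at the start of Aim 1: "These analyses will allow us to identify common and differential brain predictors of placebo effects on behavioral (pain report" outcome) and on the neurobiological outcomes. No test of difference is attached to it. Under Multiple comparisons and power, the protocol says that with N = 600 "we have 80% power with whole-brain FWER correction to detect correlations with placebo analgesia of" at least 0.22. That statement concerns brain maps; NPS and SIIPS are single scores per person, and no threshold is given for correlating them with pain report. The SAP covers thermal pain ratings only and mentions neither signature; its alpha of 0.05 is set for that model.

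**The concern.** If SIIPS passes a threshold and NPS does not, the two correlations may still be equal, with sampling error placing one on each side of the line. The expected pattern would then be reported as a dissociation, and a mechanism inferred from it, although nothing had tested the dissociation. A non-significant NPS result is also weak evidence of no relation: with N = 600 and two-sided .05, it is compatible with an upper 95% limit of up to about r = .16. At stake is the main mechanistic contrast of Analysis 1a: whether reported analgesia reflects bias in reporting or a change in nociceptive processing.

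**Working it through.** **Inputs from the documents.** N = 600; 80% power at r = 0.22 under whole-brain correction; 80% power at r = 0.65 with N = 50 (all from Multiple comparisons and power).

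**Assumptions not in the documents.** Two-sided tests; equal true correlations r of pain report with each signature; correlation c between the two estimates of 0 to .5 (for small r, close to the correlation between the signatures themselves); variance inflation from twin pairs of 1.0-1.1; equal reliability of the signatures.

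**1. The protocol's own power figure.** No per-test alpha is given, so the figure can only be solved backwards. On the Fisher scale, atanh(.22) × √597 = .2237 × 24.43 = 5.465. Subtracting .842 (80% power) gives a critical z of 4.62, or two-sided alpha of about 3.8 × 10⁻⁶. As a check, N = 50 at that threshold needs tanh(5.465/√47) = .66, against the protocol's "correlations must be $r = 0.65$ or larger to be detectable with 80% power". The two figures agree roughly and are not disputed.

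**2. Chance of the pattern when the true correlations are equal.** Let m = atanh(r) × √597. With independent estimates, the chance that SIIPS is significant and NPS is not is essentially p(1 − p), where p = Φ(m − 1.96). At r = .08, m = 1.96 and p = .50, giving .50 × .50 = 25%, the maximum. At r = .10, m = 2.45 and p = .69, giving .69 × .31 = 21%. For c = .5 the same probability comes from a bivariate normal.

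| True r (both) | c = 0 | c = .5 |
|---|---|---|
| .06 | 21% | 15% |
| .08 | 25% | 17% |
| .10 | 21% | 15% |
| .12 | 14% | 10% |
| .15 | 4% | 3% |
| .22 | 0.02% | 0.02% |

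With variance inflation of 1.1, the r = .15 row becomes 6% and 4%, and the r = .22 row stays below 0.1%. Simulating 300 pairs with a within-pair correlation of .4 moved the results by about 2 points at most.

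**3. The same at the implied whole-brain threshold (z = 4.62).** At r = .22, p = .80, so .80 × .20 = 16% for c = 0, and 11% for c = .5. An observed NPS correlation of up to tanh(4.62/24.43) = .19 would count as not significant.

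**4. Adding a direct comparison.** The statistic is (z_SIIPS − z_NPS)/√(2 − 2c), with each z in standard-error units, tested at two-sided .05. Requiring the pattern and a significant difference gives about 2-2.5% at r = .06-.10. When pairs were simulated with a within-pair correlation of .4, an ordinary dependent-correlation test gave up to 3.6%, which is why families should be resampled.

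**5. Power of the comparison (N = 600, inflation 1.0).** For .10 vs 0 with c = 0: 2.452/1.414 = 1.73, and Φ(1.73 − 1.96) = 41%.

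| True SIIPS r vs NPS r | c = 0 | c = .5 |
|---|---|---|
| .22 vs 0 | 97% | >99% |
| .15 vs 0 | 74% | 96% |
| .10 vs 0 | 41% | 69% |

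**6. Would an equivalence bound do instead?** Take |r| < .15 as an illustration. The 90% interval lies inside it when |z_NPS| < 3.693 − 1.645 = 2.05, slightly looser than non-significance (1.96). At equal r = .08, NPS passes in Φ(2.05 − 1.96) = 54% of studies, so a significant SIIPS with NPS inside the bound occurs in .50 × .54 = 27% (c = 0). Over r = .06-.10 the range is 16-27%, or 13-23% with inflation of 1.1. The bound alone does not remove the problem.

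**The case against.** Four points on the other side have force.

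- **The inference does not rest on this contrast alone.** Analysis 1a also expects a relation with anticipatory fronto-parietal activity. Decision bias is also measured directly by the perceptual tasks in A.2.1, which Analysis 1c relates to analgesia. The text is a hypothesis with a stated alternative, not a decision rule. This stands, and it rules out saying that the conclusion depends wholly on the SIIPS-NPS pattern. The fronto-parietal requirement can only lower the chance of the full pattern, but it cannot tell SIIPS from NPS.
- **The plan is not confined to tests against zero.** A reader might infer that each relation is only tested for significance, but the documents name no test for these two scores at all. Analysis 2b applies a bivariate ACE model to analgesia with NPS and SIIPS and estimates genetic and environmental correlations. That is useful estimation, but it treats each relation separately and does not compare them.
- **The false pattern is not generally frequent.** A reader might take the 25% as typical. It is the peak, at about r = .08 with independent estimates. At the protocol's r = .22 and alpha .05 it all but vanishes. The higher figure there needs the whole-brain threshold, and the documents do not say that it applies.
- **A 5% error rate is the wrong yardstick.** The pattern has one direction, and a two-sided difference test errs in that direction 2.5% of the time. The working compares like with like.

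A reader might also extend the point to Analysis 1c, which says "Negative results will also be very important, as several companies are currently investing in personality-based predictors for clinical settings". The documents do not support that. Analysis 1c uses five-fold cross-validated prediction, which yields an estimate of accuracy, and it states no rule that non-significance means the measures are not viable.

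**Conclusion.** The point holds in limited form. Analysis 1a attaches a mechanistic meaning to a relation with SIIPS and none with NPS, alongside a fronto-parietal relation. The documents give no test that the two relations differ and no threshold for either. Under equal true correlations the pattern can arise in up to about 1 in 4 studies, but only in a band of small r at alpha .05, or around r = .15-.22 if the implied whole-brain threshold were used. These figures rest on N = 600 and on the assumed correlation between estimates, twin inflation and equal reliability set out above. The matter concerns the reading of a secondary mechanistic contrast, not the SAP's main analysis.

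**What to change.** In Analysis 1a, or in a short SAP addition:

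- State the significance threshold for the score-level correlations of pain report with NPS and SIIPS.
- Claim a SIIPS-versus-NPS dissociation only if a direct test of the two dependent correlations is significant, with families resampled to respect the twin pairs.
- Report the NPS correlation with its confidence interval, and do not call it unrelated because it is non-significant.
- An equivalence bound is optional and for the investigators to choose and justify. It may accompany the difference test but not replace it.

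The cost is a few lines of text and one extra test, with no new data. Power is limited for small differences (41-69% for .10 vs 0), so some true dissociations will stay unresolved. A significant difference could also reflect unequal reliability of the two signatures, which should be considered when it is interpreted.
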